6.6.2 DAY 28 POST ENROLLMENT

This visit may be done via telephone call or office visit. Please record the following information on day 28 (+7 days) following enrollment:

- Presence / date and setting of mechanical ventilation (since last visit)
- Presence / date and settings of renal replacement therapy (since last visit)
- Serious Adverse events (since last visit)

- Serum creatinine (if an office visit takes place)
- ICU discharge date
- Hospital discharge date

6.6.3 DAY 60 POST ENROLLMENT

This visit may be done via telephone call or office visit. Please record the following information on day 60 (+7 days) following enrollment:

- Presence / dates of mechanical ventilation (since last visit)
- Presence / dates of renal replacement therapy (since last visit)
- Serious Adverse events (since last visit)
- Serum creatinine (if an office visit takes place)

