Study Endpoints	
In this Pilot study four domains of interest have been designated. The four domains are:
 
 • Patient Safety: Safety Endpoint Measures include adverse events, laboratory safety parameters, vital signs, EKG, ventilation status and hemodynamic variables. • Clinical Efficacy: The Primary Clinical Efficacy Endpoint Measure is in-hospital; 28 and 60-day all-cause mortality. Time to renal recovery and necessity for chronic dialysis up to day 60 will also be determined. Additional efficacy endpoints include time to intensive care unit (ICU) discharge, and time to hospital discharge. • Device Integrity and Performance: The Endpoint Measure is SCD use without failure. This measure will help assess the integrity and performance of the SCD device. • SCD Mode of Action: Exploratory Endpoint Measures will include inflammatory cytokines, cell activation parameters and biomarkers at clinical sites with this capability. The analysis will be performed at a central laboratory.
Assessment of Device Integrity and Performance	
Criteria for assessment of device integrity and performance include:
 
 • Significant Clotting within the Device as assessed by visual inspection. • Evidence of leakage (i.e., cracking/breakage of a port, connector, hemofilter cartridge or tubing).

	
 Any unforeseen malfunction that results in the need for discontinuation.
Study Populations	Pediatric patients with a body weight (BW) between ≥ 10 and ≤ 20 kg receiving care in the Intensive Care Units of each participating hospital will be screened daily and identified for participation in the trial.
Study Design	This is an open-label, multi-center Pilot study.
Approximate Number of Subjects	Up to 10 patients will be enrolled in this study.
Approximate Number of Centers	Up to 7 Clinical Centers in the United States will participate in this study.
Duration of Subject Participation	Each patient will be followed for 60 days following enrollment.

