	
 4. Presence of preexisting advanced chronic renal failure (i.e., ESRD) requiring chronic renal replacement therapy prior to this episode of acute kidney injury or with pre-existing chronic kidney disease (CKD) defined as an eGFR<30 ml/min/1.73m². Patients who have never seen a pediatric nephrologist will be assumed not to have pre-existing CKD. 5. AKI occurring in the setting of burns, obstructive uropathy, scleroderma renal crisis, atheroembolism, functional or surgical nephrectomy, cyclosporine, or tacrolimus nephrotoxicity. 6. Metastatic malignancy which is actively being treated or may be treated by chemotherapy or radiation during the subsequent three month period after study therapy. 7. Chronic immunosuppression with the exception of corticosteroids up to a dose of 10 mg per day. 8. Known positive HIV or AIDS or COVID-19 9. Current Do Not Attempt Resuscitation (DNAR), Allow Natural Death (AND), or withdrawal of care status, or anticipated change in status within the next 7 days. 10. Patient not expected to survive 28 days because of an irreversible medical condition. (This is not restrictive to AKI, and may include situations such as the presence of irreversible brain damage, untreatable malignancy, inoperable life threatening condition, or any condition to which therapy is regarded as futile by the PI.) 11. Any medical condition that the Investigator thinks may interfere with the study objectives. 12. Treating clinician does not feel it is in the best interest of the patient 13. Platelet count <15,000/mm³ at time of screening. 14. Concurrent enrollment in another interventional clinical trial. Patients enrolled in clinical trials where only measurements and/or samples are taken (NO TEST DEVICE OR TEST DRUG USED) are allowed to participate. 15. Use of any other investigational drug or device within the previous 30 days. 16. Use of an AN-69 hemofilter membranes
Evaluation Plan	The primary evaluation of this study will be safety and all-cause mortality or dialysis dependency through 60 days post-enrollment. Additional endpoints will be time on CRRT, total ICU and hospital days. Mortality and dialysis dependency rates will be compared to historical controls.

LIST OF ABBREVIATIONS

ACD-A	Anticoagulant Citrate Dextrose- Formula A
AE	Adverse Event
AKI	Acute Kidney Injury
AIDS	Acquired Immunodeficiency Syndrome
AND	Allow Natural Death
ARDS	Acute Respiratory Distress Syndrome
ARF	Acute Renal Failure

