3.2 STUDY ENDPOINT

In this Pilot study four (4) domains of interest have been designated. The four (4) domains are:

1. Patient Safety: Safety Endpoint Measures include adverse events, laboratory safety parameters, vital signs, EKG, ventilation status and hemodynamic variables.
2. Clinical Efficacy: The Primary Clinical Efficacy Endpoint Measure is in-hospital; 28 and 60-day all-cause mortality. Time to renal recovery and necessity for chronic dialysis up to day 60 will also be determined. Additional efficacy endpoints include time to intensive care unit (ICU) discharge, and time to hospital discharge.
3. Device Integrity and Performance: The Endpoint Measure is SCD use without failure. This measure will help assess the integrity and performance of the SCD device.
4. SCD Mode of Action: Exploratory Endpoint Measures will include inflammatory cytokines, cell activation parameters and biomarkers at clinical sites with this capability.

Endpoints are defined as:

ALL-CAUSE MORTALITY:

All-cause mortality is defined as in-hospital, 28-day and 60-day all-cause mortality.

DIALYSIS DEPENDANCY AT DAY 60:

Dialysis dependency at day 60 is defined as patient not receiving any form of intermittent or continuous renal replacement therapy at or within 3 days of 60 days post enrollment in the study with no plans for additional intermittent or continuous renal replacement therapy.

PATIENT SAFETY:

Adverse events, laboratory safety parameters, vital signs, EKG, ventilation status and hemodynamic variables.

DURATION OF RENAL SUPPORT:

The duration of renal support will be defined as the numbers of days from the initiation of renal replacement therapy (start of observation period) to final dialysis treatment. Duration of renal support will be censored if the patient is still dialysis dependent at the time of death or are dependent at day 60.

RECOVERY OF RENAL FUNCTION:

Recovery of renal function will be defined as lack of need for continuous dialysis support on day 28, and will be classified as yes or no at day 28.

Subjects who were alive at day 28 will be included in the analysis.

Patients who remain dialysis dependent at study completion (day 60) or time of death will be categorized as having no recovery of renal function.

ASSESSMENT OF DEVICE INTEGRITY AND PERFORMANCE

Criteria for assessment of device integrity and performance include:

- Significant Clotting within the Device as assessed by visual inspection

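### ICU and hospital discharge dates are listed at the Day 28 contact but not at Day 60, so the discharge endpoints go uncollected after Day 28 (+7 days) although follow-up runs to Day 60

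*Combined protocol and SAP*

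**What the plan says.** All references are to the combined protocol and SAP.

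- **Endpoints.** Section 3.2 states "Additional efficacy endpoints include time to intensive care unit (ICU) discharge, and time to hospital discharge". The Evaluation Plan in the synopsis adds "Additional endpoints will be time on CRRT, total ICU and hospital days". On mortality, Section 3.2 states "All-cause mortality is defined as in-hospital, 28-day and 60-day all-cause mortality". It gives no end date for the in-hospital component, and no horizon or censoring rule for the discharge endpoints.
- **Follow-up.** The synopsis states "Each patient will be followed for 60 days following enrollment".
- **Day 28 contact (Section 6.6.2).** The list opens "Please record the following information on day 28 (+7 days) following enrollment" and includes "ICU discharge date" and "Hospital discharge date".
- **Day 60 contact (Section 6.6.3).** The list opens "Please record the following information on day 60 (+7 days) following enrollment". It has four items: ventilation, renal replacement therapy, serious adverse events, and creatinine if there is an office visit. Neither discharge date appears.
- **Schedule of events (Section 6.3).** There is no row for discharge or vital status at any visit.
- **Deaths.** Section 9.2 makes death a serious adverse event. Section 9.7.2 records serious adverse events to Day 60 and has them reported within 24 hours of knowledge.

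**The concern.** Three named endpoints depend on discharge dates: time to ICU discharge, time to hospital discharge, and total ICU and hospital days. The protocol stops asking for those dates at the Day 28 contact, although the study stays in touch with each family until Day 60.

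The children affected are not a random subset. They are those with the longest stays, so the upper end of the length-of-stay distribution goes unobserved, and that is where a benefit or harm on recovery time would show. With at most 10 children, each censored stay weighs heavily in any summary.

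A smaller consequence concerns in-hospital mortality, which is part of the primary efficacy measure and is to be compared with historic data under Section 3.1. For a death after the Day 28 contact, neither visit list shows whether the child was still an inpatient.

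**Working it through.** The plan gives no figure to reproduce here: there is no sample-size calculation, and no expected share of children still in hospital at Day 28. The check is mainly a comparison of lists.

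**1. The two contacts side by side**

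| Item | Day 28 (6.6.2) | Day 60 (6.6.3) |
|---|---|---|
| Mechanical ventilation | listed | listed |
| Renal replacement therapy | listed | listed |
| Serious adverse events | listed | listed |
| Creatinine, if office visit | listed | listed |
| ICU discharge date | listed | not listed |
| Hospital discharge date | listed | not listed |

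The first four items are repeated at Day 60 and the two discharge dates are dropped. Daily data collection ends earlier still, at 120 hours after SCD treatment or at ICU discharge if sooner (Section 6.6.1).

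**2. Follow-up time not covered**

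- Contact held on Day 28: 60 − 28 = 32 days; 32/60 = 53% of follow-up.
- Contact held at the end of its window: 28 + 7 = Day 35; 60 − 35 = 25 days; 25/60 = 42%.

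**3. Room to leave hospital before the Day 28 contact**

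A full course is 240 hours (Section 6.5), and the daily post-treatment period is up to 120 hours (Section 6.6.1). Together that is 360 hours, or 15 days. Counting from the start of SCD, a child who uses both in full has 28 − 15 = 13 days left before Day 28, or 35 − 15 = 20 days before the end of the window. Later discharges are therefore plausible, but this does not give their frequency.

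**4. Number of children affected (assumed share)**

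Let p be the share still in hospital at the Day 28 contact. The documents give no value, so p is an assumption shown over a range. With n = 10 children treated as independent:

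- expected number = 10p
- chance of at least one = 1 − (1 − p)^10

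| Assumed p | Expected number of 10 | Chance of at least one |
|---|---|---|
| 10% | 1 | 1 − 0.9^10 = 65% |
| 30% | 3 | 1 − 0.7^10 = 97% |
| 50% | 5 | 1 − 0.5^10 = 99.9% |

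**5. What happens to in-hospital mortality**

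- Death by the Day 28 contact: discharge dates are listed at that contact, so inpatient status can be worked out.
- No fatal event by Day 60: the child did not die in hospital by Day 60. A missing discharge date does not change that.
- Death between the Day 28 contact and Day 60: the death is captured as a serious adverse event, but whether it came before or after discharge depends on what the event report says.
- In-hospital death after Day 60: not observed, because follow-up has ended. A Day 60 discharge field would only flag which children were still inpatients.

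Only the third group is left ambiguous by the missing fields.

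**The case against.** The strongest reply is that this is an unlisted field and not lost data. Section 6.6.3 is a protocol list; the case report forms are not in the documents and may carry the dates. A discharge date is a routine chart entry, and Section 13 gives monitors access to hospital charts on request. A reader might infer that the discharge endpoints cannot be completed at all. The documents do not support that. What stands is that the protocol does not ask for the dates after the Day 28 contact, and later chart retrieval across up to 7 centers is a weaker safeguard than a listed field.

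A second reply is that no horizon is stated for the discharge endpoints, so a Day 28 horizon may have been intended. The text states no such cut-off either. Section 3.2 censors duration of renal support at Day 60, and Section 6.6.3 carries the other clinical items forward, so an oversight is the more natural reading, though not a proven one. Under either reading the horizon and censoring rule need to be written down.

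A third reply is that these are additional endpoints in an unpowered pilot whose primary objective is safety. That is true and limits the importance of the point. It does not remove it, because the correction is nearly free.

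A reader might also infer that in-hospital mortality is undetermined for every child still in hospital at Day 28. That does not follow: deaths to Day 60 are captured, 28-day and 60-day mortality are unaffected, and the ambiguity is confined to a death after the Day 28 contact. Even then, the event report may settle it; its form is not in the documents.

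**Conclusion.** The omission is real and worth correcting. As written, time to ICU discharge, time to hospital discharge and total ICU and hospital days are not collected after the Day 28 (+7 days) contact and can only be censored there. That leaves 25 to 32 of the 60 follow-up days uncovered, for the longest-stay children. If 10-50% are still in hospital at that contact, 1-5 of 10 would be expected to lack a listed hospital discharge date. That range is an assumption.

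The effect on in-hospital mortality is narrow: a child who dies after the Day 28 contact, whose inpatient status would rest on the serious adverse event report. The separate lack of a stated end for in-hospital mortality is a matter of definition, to be settled in the same edit. The conclusion assumes that the case report forms follow the protocol lists, which the documents do not show.

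**What to change.** - In Section 6.6.3, and as rows in the Section 6.3 schedule, add the ICU discharge date, the hospital discharge date, and vital status with inpatient status at death.
- In Section 3.2, state that the discharge endpoints are censored at Day 60 for children still in the ICU or hospital, and that in-hospital mortality is assessed through Day 60.
- Use the same horizon for the registry controls where their data allow. The documents do not show that the registry holds discharge and death timing in a compatible form, so confirm this before the comparison is specified.

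The cost is a few extra fields at an existing contact and a short addition to Section 3.2. No new visit is needed.

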7. TREATMENT INTERRUPTIONS – DISCONTINUATION CRITERIA

7.1. TREATMENT DISCONTINUATION CRITERIA

Subjects may be withdrawn from therapy prior to hour 240 for a variety of reasons. When therapy is discontinued prior to hour 240, the follow-up period will immediately begin and data will continue to be collected per protocol.

The Principal Investigator will assign a primary reason for therapy termination utilizing the categories listed in 7.2 and 7.3 below, and if appropriate, one or more subcategories. The Principal Investigator will notify the Sponsor or designee within 24 hours of withdrawal of participation.

7.2. CLINICAL CRITERIA:

1. Improvement in Clinical Status

If a subject's condition improves (e.g. renal condition has improved to the extent that CRRT can be discontinued or hemodynamic status has improved so that the dialysis modality can be changed from CRRT to IHD) treatment may be discontinued before the 240 hour treatment period. The decision to discontinue treatment based upon improvement in clinical status will be made by the Principal Investigator.

2. CRRT related events

Such as inability to maintain vascular access based upon PI's clinical assessment. Includes failure of the CRRT device and/or circuit that requires treatment to be discontinued prior to hour 240 of therapy.

3. SCD related medical events

Such as persistent leukopenia, neutropenia or thrombocytopenia based upon PI's clinical assessment of relationship to SCD.

4. SCD Failure/Malfunction

Any failure of the SCD that requires treatment to be discontinued prior to hour 240 of therapy e.g. clotting or evidence of leakage in the SCD or inability to maintain a patent circuit.

5. Death or withdrawal of life support**6. Regional Citrate Anticoagulation Intolerance**

All subjects must be able to tolerate and achieve satisfactory regional citrate anticoagulation. Tolerance of regional citrate anticoagulation is defined as achieving:

- Two (2) consecutive circuit ionized calcium levels of < 0.40 mmol/L (or < 1.6 mg/dL),
- At least 30 minutes apart, and
- Within the first 12 hours of SCD initiation.

If unable to achieve the specific circuit ionized calcium levels within the time frame above, treatment with the SCD must be discontinued. The subject will progress on to the post-SCD follow up period, unless the subject and/or legal guardian withdraws consent for the study.

7. Hematologic Events

- Persistent leucopenia, neutropenia, thrombocytopenia based upon PI's clinical assessment
- Absolute neutrophil count less than 500 mm³ will be an indicator for therapy termination
- Platelet count less than 30,000 mm³ after transfusion of 6 units of platelets

8. Other

Any other reason that the Principal Investigator deems appropriate for discontinuation from the SCD Treatment period must be documented.

7.3. NON-CLINICAL CRITERIA:**• Withdrawal of participation from SCD treatment period**

Subjects may withdraw their consent to participate in the study observation period at any time. If the subject wishes to remain in the clinical study, the follow-up period will immediately begin at the termination of SCD treatment period. All data will continue to be collected per protocol.

The Principal Investigator will notify the Sponsor or designee within 24 hours of withdrawal of participation.

• Withdrawal of consent

If a subject or legal representative withdraws consent, all protocol related activities will be immediately discontinued. If study therapy (CRRT+SCD) is being administered at the time of withdrawal, normal procedures will be followed for CRRT+SCD therapy discontinuation (please see SCD Operator's Manual). No further study activity will be conducted.

The Principal Investigator will notify the Sponsor or designee within 24 hours of withdrawal of consent.

8. CLINICAL TRIAL TERMINATION CRITERIA

The Sponsor reserves the right to terminate the clinical trial for safety or administrative reasons at any time. If the Sponsor, Principal Investigator, Data Safety Monitoring Board (DSMB), Institutional Review Board (IRB), or Food and Drug Administration (FDA) officials discover conditions during the study indicating that the trial or participation by a clinical site should be discontinued, this action may be taken after appropriate consultation between the Sponsor and the Investigators.

Conditions that may warrant discontinuation of the trial at a specific clinical site may include the following:

- Failure of the Investigator to enroll patients into the trial at an acceptable rate (as defined and agreed upon between the Investigator and the Sponsor).
- Failure of the Investigator to comply with the pertinent FDA regulations.
- Submission of false information by the Investigator from the research facility to the Sponsor or the FDA.
- Failure to achieve and maintain post filter iCa levels of <0.40 mmol/L

Conditions that may warrant discontinuation of the trial may include, but are not limited to, the following:

- Discovery of an unexpected, serious or unacceptable risk to the patients enrolled in the study.
- Decision on the part of the Sponsor to suspend or discontinue testing, evaluation or development of the study product at any time.

9. SAFETY

9.1. ADVERSE EVENTS

An Adverse Event is any sign, symptom, illness, clinically significant abnormal laboratory value or other adverse medical event that appears for the first time or worsens in a subject during this clinical study, regardless of whether or not it is considered related to the device.

Anticipated adverse events that may occur during CRRT include:

- thrombocytopenia
- hypo- or hypernatremia
- hypo- or hyperkalemia
- hypo- or hypercalcemia
- hypo- or hyperglycemia
- other electrolyte imbalance
- air embolism
- hypotension
- hypertension
- hemolysis
- increased oxygenation requirements
- fatigue
- dyspnea
- muscle spasm
- myalgia
- nausea
- vomiting
- fluid imbalance
- leukopenia
- arrhythmias
- hypothermia
- hyperthermia
- lactic acidosis
- temporary decrease in cardiac output or cardiac index
- disruption of skin integrity
- paresthesia
- tetany
- altered mental status
- bleeding
- shock
- infection
- bacteremia
- laryngospasm
- seizure
- death

Anticipated AEs associated with the addition of SCD to CRRT include:

- neutropenia
- thrombocytopenia
- hypotension
- hypo- or hypercalcemia
- alkalosis
- clotting within the device
- leakage due to cracking or breakage

9.2. SERIOUS ADVERSE EVENTS

Any Adverse Event, whether considered study-treatment related or not, which fits any of the criteria below, is considered a serious adverse event (SAE):

- Results in death
- Is life-threatening (meaning that the patient was at risk of death at the time of the event; this does not refer to an event which might have caused death if it had occurred in a more severe form)
- Requires in-patient hospitalization or prolongs the existing hospitalization
- Is a persistent disability/incapacity
- Is a congenital anomaly or birth defect
- Is considered an important medical event by the Principal Investigator (e.g., surgery, return to ICU, emergency procedures)

9.3. UNANTICIPATED ADVERSE DEVICE EFFECT

Unanticipated adverse device effect (UADE) is any serious adverse effect on health or safety, any life-threatening problem or death caused by, or associated with a device, if that effect, problem, or death was not previously identified in nature, severity, or degree of incidence in the application; or any other unanticipated serious problem associated with a device that relates to the rights, safety, or welfare of subjects. The Sponsor-Investigator will report UADEs to the FDA as they occur (e.g., no later than 10 working days after the Sponsor Investigator first receives notice of the effect), as mandated by 21 CFR 812.150(b)(1).

